## ***G2 Description of usual care PAT and HEALTH interventions***

### **2.a Description**

Given the national scale of PAT and the considerable variability between sites and participants, PAT curricula are primarily hands on, including dynamic interactions and role-playing. This allows for adaptation at the level of the mother-parent educator relationship, where the parent educator is able to tailor the program to meet the mother's context. Section 2.d provides additional detail.

## 2.b Usual care description

Participants at usual care PAT sites will receive the Foundational (usual care) curriculum that uses a strength-based, solution-focused model. It includes 60-minute home visit plans that focus on 1) rapport building (e.g., reflective questions to get to know the family such as “What did you notice about your child’s development?”), 2) development-centered parenting (e.g., comparing and ordering for math skills), 3) parent-child interaction (e.g., measuring dried beans), 4) family well-being (e.g., address needs in the family’s physical and emotional environment such as “Who do you think supports your child to be happy and successful?”), and 5) closing/reinforcement and follow-up plans (e.g., feedback on goals, praise for success). The frequency and number of visits are based on the family’s needs and preferences.

## 2.c HEALTH description

Participants at HEALTH (intervention) sites receive the Foundational curriculum + evidence-based lifestyle change strategies to prevent weight gain and promote weight loss embedded within and delivered as part of home visits. The HEALTH intervention is guided by PAT’s strength-based, solution-focused model and a socio-ecologic approach recognizing the protective and interactive influences on women across multiple levels.

A detailed sample of the curricular materials unique to the HEALTH intervention are included in Appendix A. In addition to the usual care PAT curriculum content, goal setting related to healthy weight, and the importance of parental modeling of healthy eating and physical activity are incorporated throughout the discussion and visit. Content mirrors the structure of the Foundational curriculum described above, but is enhanced to embed lifestyle change as the following example illustrates: 1) rapport building (e.g., reflective questions to get to know the family such as “What did you notice about your child’s development + What did you notice about your families eating?”), 2) development-centered parenting (e.g., comparing and ordering for math skills + healthy portion size), 3) parent-child interaction (e.g., measuring food in appropriate portion size), 4) family well-being (e.g., address needs in family’s physical and emotional environment such as “Who do you think supports your child to be happy and successful? + What could you do at home to make it easier to eat healthier portions?”), and 5) closing/reinforcement and follow-up plans (e.g., feedback on goals, praise for success). Other objectives include skill building and strategies to address: reduction of high-sugar beverages, substituting healthy for unhealthy foods, portion control, and eating patterns. Physical activity goals encourage a total of 150 minutes (2.5 hours) of moderate-intensity exercise (e.g., brisk walking) and/or lifestyle activity per week. HEALTH participants will be provided pedometers, allowing them to track and self-monitor their steps.

## 2.d HEALTH dose

Intervention dose. HEALTH may be delivered over 24 months via a (1) core and (2) maintenance phase. Modeled after the Diabetes Prevention Program (DPP) and various effective DPP adaptations, the visits begin with greater frequency, and

taper. HEALTH was effective with families receiving, on average, 23 visits over two years, with 39% of families receiving <15 visits, 36% of families receiving  $\geq 25$  visits, and 15% receiving  $>30$ . Consistent with PAT practice, the frequency and number of visits are determined by the family's needs and preferences, therefore the dose structure for HEALTH is flexible. A sample number of visits is provided in *Table 1*, but will likely differ by family (as was the case in the effectiveness trial) so that each family gets what they need in terms of content, number of visits, and visit frequency. The core phase (months 1-6) is the most intense and structured phase, delivered via  $\sim 13$  home visits. During this phase, participants are taught basic information about healthy eating and physical activity and are given the opportunity to practice related behavioral skills during home visits (*see lesson topics and examples in Table 1*). During this time the parent educators and mothers learn how to best work together to achieve study goals. The maintenance phase (months 7-24) reinforces lessons learned in the core phase while assisting participants in focusing on issues of relevance and problem-solving via 10 home visits. As PAT is designed to be a universal program, HEALTH was also designed to be universal; for example, while the HEALTH program stresses reducing sugar-sweetened beverage intake, parent educators tailor this to the specific types of beverages women in different cultures drink (e.g., sodas, Kool-Aid, Agua Fresca, orangeade).

## 2.e HEALTH training curriculum (implementation strategy)

We will use PAT's existing infrastructure to deliver our implementation strategy, the HEALTH training curriculum. This includes:

Training materials used in the HEALTH effectiveness trial and developed with the input of PAT National Center, will be formulated into the type of curriculum manual PAT parent educators are accustomed to receiving.

PAT parent educators will be trained to deliver HEALTH through a specialty training delivered by PAT National Center. In preparation for the current proposal, we worked with PAT National Center to harmonize the HEALTH training curriculum with the organization's usual practice and training infrastructure. The protocol may be delivered through an interactive training that includes seven components: 1) HEALTH background and rationale, 2) guidelines for healthy weight behaviors, 3) overview of the HEALTH protocol, 4) the importance of the mother's lifestyle and influence on child weight and development, 5) role-play practice sessions with other parent educators, 6) instruction on the use of self-monitoring tools and 7) feedback from trainers. Consistent with PAT training protocols we have successfully implemented, HEALTH educators must complete a posttest reflecting training objectives. A pretest will be available to frame training. Trainees must receive  $\geq 90\%$  correct on the posttest before delivering the intervention to participants.

[figure not shown]
Ongoing consultation will include 'booster' sessions, consistent with PAT 'communities of practice'. PAT educators may receive training and supervision by the research coordinator (dietitian and PAT parent educator) and by a parent educator with experience in similar trials. Parent educators may receive continuing education credits (required by PAT for all parent educators) for participating in the HEALTH training curriculum.

## H Study Procedures

## H1 Screening for Eligibility

[figure not shown]
**Mothers:** Screening for mothers will occur in two phases. First, data collectors (study team members) will screen potential participants by phone to ascertain self-reported height and weight, to determine eligibility. If the mother is eligible based on this screening, they will be offered a baseline visit. These visits may occur in the woman's home, some other location she prefers (e.g., library, doctor's office, PAT site), or at PAT site. At this visit, the data collector will assess height and weight to assure the mother's BMI is within the eligibility range. The procedures for these participants are outlined in Figure 1. Given in-person procedures are not possible during COVID-19 physical distancing, alternate procedures are outlined in Appendix C.

Figure 1. HEALTH D&I Measurement: Participants (Intervention and Usual care)

**PAT staff:** as there are no exclusion criteria, no screening is required. The procedures for these participants are outlined in Figure 2.

Figure 2. HEALTH D&I Measurement: Parent Educators & Site Leaders (Intervention and Usual Care)

## H2 Schedule of Measurements

Mothers: The flow of participants is outlined in Figure 1. After the mother consents to study participation, the data collector will conduct baseline measures (i.e., anthropometry, blood pressure, behavior measures, home environment measures); data collection is summarized in Table 1 (below). Data collectors will conduct anthropometry and blood pressure measures and mothers will be asked to complete surveys for data collection. Data collection will occur again at 12 and 24 months (conducted by the data collector at all time points). As randomization will be at the PAT site level, data collection will be the same for both HEALTH and usual care with one exception. Mothers will be asked to complete an acceptability survey along with their 12 and 24 month measures. Given in-person procedures are not possible during COVID-19 physical distancing, alternate procedures are outlined in Appendix C.

During home visits, parent educators may (with participant consent) record the visits so that fidelity to and adaptations from the intervention can be monitored.

Table 1. Summary of Measures

Time point	Acronym	SC	BL	M12	M24
Day (window, ± days from randomization)				≤180	
Day (window, ± weeks from BL)				365±90	730±90
MOTHER-LEVEL DATA					
Telephone Screening (self-report HT, WT → consent)		•			
Demographic and Socio-Economic Characteristics	DEM		•		
Anthropometrics					
Height	HT		•		
Weight	WT		•	•	•
Blood Pressure	BP		•	•	•
Waist Circumference	WC		•	•	•
Safety monitoring (excessive weight loss - >15%)					
Behavior					
NHANES Dietary Screener Questionnaire (from			•	•	•

HEALTH				
IPAQ ( http://uacc.arizona.edu/sites/default/files/ipaq_english_telephone_short.pdf )		•	•	•
Home Environment				
Kegler_2014_The influence of home food environments on eating behaviors of overweight and obese women		•	•	•
HEALTH Effectiveness Trial Items (SES, race/ethnicity, norms)		•	•	•
Individual Parent-Level Satisfaction Measure (RE-AIM measure: acceptability)				•
Testing performed by the data collectors; respondent self report				

Mothers in the HEALTH group will be purposively selected to be representative of those with varying (high, middle, low) scores on the quantitative measures for acceptability (acceptability survey). Interviews will be completed by phone, and will be digitally recorded. We anticipate interviews to assess implementation outcomes (acceptability, appropriateness, and feasibility) will last 45-60 minutes.

Mothers will receive PAT services throughout the 24 months, consistent with PAT practice; mothers served by sites randomized to HEALTH will receive PAT from parent educators trained in the HEALTH curriculum, and those served by usual care PAT sites will receive usual care PAT. Once final data collection occurs at 24 months, no additional follow-up will occur.

PAT staff: The flow of participants is outlined in Figure 2. After PAT staff consent, those at sites randomized to HEALTH may be trained in the HEALTH training curriculum through PAT's existing training infrastructure. Staff at sites randomized to usual care will continue to provide usual care PAT, and will be able to receive the HEALTH training curriculum at the end of the study. Staff at both sites will be asked to record visits with study participants so that fidelity to and adaptations from the intervention can be monitored and to complete visit checklists after each visit with a participating mother documenting visit content.

Staff at all sites will be asked to complete surveys to assess implementation outcomes (acceptability, adoption, appropriateness, feasibility, fidelity, and adaptation). Staff at sites randomized to the HEALTH training curriculum will be asked to take the surveys at enrollment/randomization (before training) and again after training. Parent educators in usual care sites will also be asked to complete the measures at baseline, upon enrollment into the study. Both sets of educators will be asked to complete the measures at the end of the intervention period, before the usual care sites receive the HEALTH training curriculum. Usual care parent educators will complete a final round of surveys after they receive the HEALTH training curriculum.

PAT staff will be purposively selected to be representative of those with varying (high, middle, low) scores on the quantitative measures for acceptability to be invited to participate in qualitative data collection. Interviews will be completed by phone and will be digitally recorded. We anticipate interviews to assess implementation outcomes (acceptability, appropriateness, and feasibility) will last 45-60 minutes. Parent educators will complete interviews after conducting HEALTH with at least three families. Following this final data collection, no additional follow-up will occur.

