### ***E2 Secondary Aims***

**Aim 2. Evaluate the HEALTH training curriculum's impact on implementation outcomes (e.g., acceptability, fidelity), at the parent educator level, when 112 parent educators (~8/site) are trained by PAT National Center.** We hypothesize that parent educators receiving the HEALTH training curriculum will:

Hypothesis 2.1 Deliver HEALTH with fidelity (adherence, quality of delivery, exposure to the intervention, and participant responsiveness or involvement). [primary]

Hypothesis 2.2 Deliver HEALTH as designed, but adapted for content, consistency, and intensity. [secondary]

Hypothesis 1.3 Rate HEALTH acceptable, appropriate, and feasible to implement in routine practice. [secondary]

**Aim 3. Characterize determinants that influence HEALTH D&I at three levels: mother, parent educator, PAT site to enhance external validity (reach and maintenance/sustainability).**

Question 3.1 Are the mothers participating in HEALTH representative of typical PAT participants?

Question 3.2 What characteristics of parent educators make them more likely to deliver HEALTH with fidelity?

Question 3.3 Are there characteristics of PAT sites that make them more likely to adopt and maintain HEALTH?

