### ***K3 Performance Monitoring***

An important outcome of the study is to monitor parent educator fidelity to the HEALTH intervention. Careful fidelity monitoring through evaluation of visit audio recordings and visit checklists will be conducted.

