### ***L2 Participant Stipends or Payments***

There are several types of incentives in the study. Participating mothers will receive \$20 for each research visit (baseline, 12-months, and 24-months). As the visit checklists are extra reporting for research purposes, parent educators (HEALTH and usual care) may receive \$10 incentives for each visit checklist completed. Parent educators participating in surveys about implementation outcomes and context may receive \$30 gift cards at each time-point. Mothers, parent educators, and site leaders participating in qualitative interviews may receive \$30 incentives.

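### The only fidelity evidence not reported by the educator is a set of visit recordings that educator and mother choose to make, with no selection rule, coverage target or check for selective recording

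*Combined protocol and SAP*

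**What the plan says.** E2 (Secondary Aims) gives as Hypothesis 2.1, tagged primary for Aim 2, that trained educators will "Deliver HEALTH with fidelity (adherence, quality of delivery, exposure to the intervention, and participant responsiveness or involvement". Question 3.2 under Aim 3 then asks which educator characteristics go with faithful delivery.

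The sources of fidelity data are described in these places:

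- **Recordings, under Mothers in H2:** "parent educators may (with participant consent) record the visits so that fidelity to and adaptations from the intervention can be monitored".
- **Recordings, under PAT staff in H2:** "Staff at both sites will be asked to record visits with study participants".
- **Checklists, H2:** the same staff are asked "to complete visit checklists after each visit with a participating mother documenting visit content".
- **Surveys, H2:** "Staff at all sites will be asked to complete surveys to assess implementation outcomes (acceptability, adoption, appropriateness, feasibility, fidelity, and adaptation".
- **Use, K3:** "Careful fidelity monitoring through evaluation of visit audio recordings and visit checklists will be conducted".
- **Payment, L2:** educators may receive $10 "incentives for each visit checklist completed". No payment for a recording is described.
- **COVID procedures, Appendix C (Intervention delivery):** completing a visit record for a virtual visit is optional for the educator.

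J3 to J5 name no fidelity score, threshold or analysis, and say nothing specific about unrecorded visits.

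**The concern.** Two of the three sources, checklists and surveys, are the educator's own account of her work. The checklist documents visit content. That can support exposure and part of adherence, but nothing suggests it gives an independent view of quality of delivery or of the mother's responsiveness. For those components the recording is the only outside evidence.

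Whether a recording exists depends on the educator making it and the mother agreeing. If visits expected to go well are recorded more often, or if less engaged educators record less, a high fidelity result cannot be told apart from selective recording.

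Question 3.2 is exposed in a second way. If the characteristics that predict fidelity also predict who records, the association is distorted as well as the average.

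**Working it through.** The plan states no fidelity figure, so there is nothing to reproduce. The check sets the sources side by side and then shows, under stated assumptions, how much an uncontrolled selection could matter.

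**1. Sources compared**

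| Source | Completed by | Visits covered, as written | Selection rule or coverage target |
|---|---|---|---|
| Audio recording | Device, started by the educator, with the mother's consent | Permitted (H2, Mothers); requested (H2, PAT staff) | None found |
| Visit checklist | Educator | Requested after every visit; optional for virtual visits (Appendix C) | Every visit, by request |
| Staff survey | Staff | Not visit-level | Not applicable |

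**2. Volume**

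Inputs: 200 HEALTH mothers (A1), and 23 visits on average over two years in the previous trial (2.d HEALTH dose).

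200 × 23 = 4,600 visits, with visit plans of 60 minutes (2.b). Actual numbers will vary, since 39% of families in the previous trial had fewer than 15 visits. Complete recording and scoring at this volume looks unlikely, but the plan does not say what share is intended.

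**3. Bounds with no assumption about direction**

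Assume each visit is either adherent or not and that recordings are scored correctly. Let c be the share of visits recorded and f the adherent share among them. The true share lies between f × c (no unrecorded visit adherent) and f × c + (1 − c) (all adherent). With f = 0.80:

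| Coverage c | Lower: 0.80c | Upper: 0.80c + 1 − c |
|---|---|---|
| 0.25 | 0.20 | 0.95 |
| 0.50 | 0.40 | 0.90 |
| 0.90 | 0.72 | 0.82 |

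The values of c and f are assumptions; the documents give neither.

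**4. Illustration with a direction**

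Let p be the true adherent share and k the recording probability for adherent visits divided by that for non-adherent visits. The share seen in recordings is pk / (pk + 1 − p). With p = 0.70 (assumed):

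| k | Observed share | Bias, points |
|---|---|---|
| 0.8 | 65.1% | −4.9 |
| 1 | 70.0% | 0 |
| 1.25 | 74.5% | +4.5 |
| 1.5 | 77.8% | +7.8 |
| 2 | 82.4% | +12.4 |
| 3 | 87.5% | +17.5 |

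At k = 2, a true 50% appears as 66.7% and a true 85% as 91.9%. Overstatement needs k > 1; at k = 1 there is none, and below 1 fidelity is understated.

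**5. Question 3.2**

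Take two groups of educators, both with p = 0.70, one with k = 1 and the other with k = 2. The recordings show 70.0% and 82.4%, a difference of 12.4 points where none exists.

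**The case against.** The case against has several good parts.

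- **Recordings are not the sole source.** A reader might infer that fidelity is scored only from visits educators pick. K3 pairs recordings with checklists, and checklists are requested after every visit. Exposure can be measured without audio. This stands, and limits the concern to what only an outside source can show.
- **The staff text is firmer.** It asks for recordings and invites no choice, and consent is needed to record in a family's home under any design. This stands, but a request without a rule or target still leaves coverage uncontrolled.
- **Silence is not a rule.** The documents do not say that whatever is supplied gets scored, and the research team could sample from recordings received. That is true. It would not repair selection at the recording stage, and it is not specified.
- **Upward bias is not shown.** A reader might infer that fidelity will be overstated by a calculable amount. For example, with a score SD of 15, a correlation of 0.3 to 0.6 between the educator's expectation and the score, and strict recording of the best-rated visits, the bias is r × SD × φ(z)/p, where p here is the fraction recorded. With φ(z)/p = 0.80, 1.27 and 1.75 it is 3.6–7.2, 5.7–11.4 and 7.9–15.8 points when a half, a quarter and a tenth are recorded. The arithmetic is right, but none of the inputs is in the documents, strict truncation is the extreme case, and a positive correlation assumes the answer.
- **Adaptation (Hypothesis 2.2) does not simply rest on recordings.** J4 describes the adaptation coding under interview transcripts, so that hypothesis is only partly exposed.
- **A rule may exist elsewhere.** Figure 2, which outlines staff procedures, is not readable in the copy reviewed. J5 has general missing-data text, but it does not mention recordings.
- **Aim 2 is secondary.** Hypothesis 2.1 states no threshold or between-arm test, and weight is untouched. This limits the stakes but does not remove them, because fidelity is that aim's primary hypothesis.

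**Conclusion.** The concern holds in a limited form. Recordings are the only described fidelity source not reported by the educator. Which visits are recorded is left to educator and mother, and the readable text has no selection rule, coverage target or check for selective recording. Followed as written, the plan could overstate fidelity under Hypothesis 2.1 and distort Question 3.2.

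The documents support no estimate of direction or size. The figures above show only that the answer depends heavily on coverage: at 90% coverage an observed 80% is pinned to within 10 points (72% to 82%), and at 25% coverage it is hardly informative without further assumptions (20% to 95%). The conclusion rests on the readable text and would change if Figure 2 or a separate fidelity manual sets a sampling rule.

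**What to change.** 1. Reconcile the two statements in H2 so that recording is either permitted or requested, in the same terms for both arms.
2. Have the research team, not the educator, choose at random which visits are scored. One option is to draw from all recordings received. This is simpler, but leaves selection at the recording stage to step 4. The other is to draw visits per mother, stratified by core and maintenance phase, with a replacement rule for drawn visits that do not occur and as little advance notice as practical, since notice invites preparation. For scale, three drawn visits per HEALTH mother would be 3 × 200 = 600, against up to 4,600. Mothers may still decline.
3. Use the per-visit checklists as the denominator. Log each visit without a recording and the reason, and report coverage by educator and site.
4. Compare checklist content between recorded and unrecorded visits. If they differ, weight the fidelity estimate by the inverse of the estimated probability of recording. Report agreement between checklist and recording where both exist.

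The cost is some coordination and analysis time, and most of the data are already planned. The adjustment is partial: checklists are self-report, may be incomplete for virtual visits, and weighting works only as far as checklist content captures what drives recording.
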